3.3 SELECTION OF TRIAL POPULATION

A total of up to approximately 120 patients may be recruited into the study. Approximately 9-12 patients will be entered into the phase Ib tolerability and safety phase of the study (escalation part) to ensure the safety of the combination therapy and determine the MTD and/or recommended phase II dose (RP2D). For the exploratory expansion cohort approximately 25 patients will be treated with BI 836845 at the MTD, and/or recommended phase II dose (RP2D) in combination with enzalutamide.

In phase II of the study, 80 patients will be randomised onto one of the two study arms, with 40 patients randomised to each arm (Arm A=40, Arm B=40).

The Phase Ib escalation part of the study will be performed in 4 or more centres. The Phase Ib expansion part of the study will be performed in 8 or more centres. The Phase II of the study will be performed in 25-30 centres globally.

A log of all patients included into the study (i.e. having given informed consent) will be maintained in the ISF at the investigational site irrespective of whether they have been treated with investigational drug or not.

Page 39 of 241

Proprietary confidential information. © 2022 Boehringer Ingelheim International GmbH or one or more of its affiliated companies. All rights reserved.

3.3.1 Main diagnosis for study entry

Patients to be included in this trial must have diagnosed and histologically, or cytologically, confirmed metastatic CRPC.

For the phase Ib dose escalation cohort and phase II cohort patients must have received and progressed after docetaxel-based chemotherapy and abiraterone treatment in any setting. Patients may, or may not, have received and failed prior cabazitaxel treatment, in any setting.

For the exploratory expansion cohort patients will have received enzalutamide and be beginning to show a rise in PSA level according to standard criteria (R13-1642), and as per section 3.3.2 (inclusion criterion #19), prior to entry into the trial. Patients must not have received prior docetaxel, cabazitaxel or abiraterone treatment, in any setting.

3.3.2 Inclusion criteria

- 1. The patient has histologically, or cytologically, confirmed adenocarcinoma of the prostate.
- 2. Male patient aged \geq 18 years old.
- 3. Patients with radiographic evidence of metastatic prostate cancer (stage M1 or D2). Distant metastases evaluable by radionuclide bone scan, CT scan, or MRI within 28 days before the start of study treatment.
- 4. Patients with a PSA ≥ 5 ng/mL.
- 5. Patients with prior surgical or chemical castration with a serum testosterone of <50 ng/mL. If the method of castration is luteinizing hormone releasing level hormone (LHRH) agonists, the patient must be willing to continue the use of LHRH agonists during protocol treatment.
- 6. Eastern Cooperative Oncology Group performance status (ECOG PS) 0 or 1.
- 7. Cardiac left ventricular function with resting ejection fraction ≥50% as determined by ECHO or MUGA.
- 8. Absolute neutrophil count (ANC) ≥1500/uL.
- 9. Haemoglobin ≥9 g/dL.
- 10. Platelets \geq 100,000/uL.
- 11. Bilirubin \leq 1.5 times the upper limit of normal (ULN).
- 12. Aspartate transaminase (AST) and alanine transaminase (ALT) \leq 2.5 times the ULN (or \leq 5 times the ULN if liver metastases are present).
- 13. Creatinine $\leq 1.5 \text{ x ULN}$.
- 14. International normalized ratio (INR) ≤ 2 and a partial thromboplastin time (PTT) ≤ 5 seconds above the ULN (unless on oral anticoagulant therapy). Patients receiving full-

Proprietary confidential information. © 2022 Boehringer Ingelheim International GmbH or one or more of its affiliated companies. All rights reserved.

dose anticoagulation therapy are eligible provided they meet all other criteria, are on a stable dose of oral anticoagulant or low molecular weight heparin (except warfarin or coumarin-like anticoagulants, which are not permitted).

15. Fasting plasma glucose < 8.9 mmol/L (< 160 mg/dL) and HbA1c < 8.0%.

Inclusion criteria only for patients entering phase Ib dose escalation and phase II:

- 16. Patients who have disease progression during, or after, receiving docetaxel and have had at least 12 weeks of treatment and in the opinion of the investigator are unlikely to derive significant benefit from additional docetaxel-based therapy, or were intolerant to therapy with this agent.
- 17. Patients who have disease progression during, or after, receiving abiraterone treatment in any setting.
- 18. Patients must have progressive disease defined as at least one of the following:
 - a. Progressive measurable disease: using conventional solid tumour criteria RECIST 1.1.
 - b. Bone scan progression: at least two new lesions on bone scan, plus a rising PSA as described in c below.
 - c. Increasing PSA level: at least two consecutive rising PSA values over a reference value (PSA #1) taken at least 1 week apart. A third PSA (PSA #3) is required to be greater than PSA #2; if not, a fourth PSA (PSA #4) is required to be greater than PSA #2.

Inclusion criterion #19 only for patients entering phase Ib expansion cohort:

- 19. Patients must be receiving continuous enzalutamide treatment and show a rise in PSA level: at least two consecutive rising PSA values over a reference value (PSA #1) taken at least 1 week apart. A third PSA (PSA #3) is required to be greater than PSA #2; if not, a fourth PSA (PSA #4) is required to be greater than PSA #2.
- 20. Archive tumour tissue is available prior to recruitment for pharmacogenomic tests.

3.3.3 Exclusion criteria

- 1. Exclusion criterion 1 is not applicable for patients enrolled after protocol version 3 (or subsequent versions) are approved.
- 2. Exclusion criterion 2 is not applicable for patients enrolled after protocol version 3 (or subsequent versions) are approved.
- 3. Prior therapy with agents targeting IGF and/or IGFR pathway.
- 4. Patients that have been treated with any of the following within 4 weeks of starting trial treatment: chemotherapy, immunotherapy, biological therapies, molecular targeted therapy, hormone therapy (except LHRH agonists and LHRH antagonists),

Boehringer Ingelheim 06 Jun 2022 BI Trial No.: 1280.8

Doc. No.: c02304008-15 Trial Protocol Version 12 Page 41 of 241

Proprietary confidential information. © 2022 Boehringer Ingelheim International GmbH or one or more of its affiliated companies. All rights reserved.

radiotherapy (except in case of localized radiotherapy for analgesic purpose or for lytic lesions at risk of fracture which can then be completed within 2 weeks prior to study treatment).

- 5. Use of any investigational drug within 4 weeks before start of trial treatment or concomitantly with this trial.
- 6. Patients that have been treated with strong CYP2C8 inhibitors, CYP2C8 inducers, within 2 weeks of starting the trial treatment.
- 7. QTcF prolongation > 450 ms or QT prolongation deemed clinically relevant by the investigator (e.g., congenital long QT syndrome). The QTcF will be calculated as the mean of the 3 ECGs taken at screening.
- 8. Patients with small cell or neuroendocrine tumours.
- 9. Patients with known or suspected leptomeningeal metastases.
- 10. Uncontrolled or poorly controlled hypertension.
- 11. Exclusion criterion 11 is not applicable for patients enrolled after protocol version 5 (or subsequent versions) are approved.
- 12. Known human immunodeficiency virus infection or acquired immunodeficiency syndrome-related illness.
- 13. Patients with epilepsy, seizures, or predisposing factors for seizure as judged by the investigator.
- 14. Patients unable to comply with the protocol as judged by the investigator.
- 15. Active alcohol or active drug abuse as judged by the investigator.
- 16. A history of allergy to human monoclonal antibodies.
- 17. Patients who are sexually active and unwilling to use a medically acceptable method of contraception, e.g. condom plus spermicide use for participating males, plus another form of birth control such as implants, injectables, combined oral contraceptives, intrauterine devices for female partners, during the trial and for at least three months after end of active therapy. Men unwilling to agree to not donate sperm while on trial drug and up to 6 months following the last dose of trial drug.

Exclusion criteria only for patients entering phase Ib dose escalation and phase II:

18. Patients that have received prior enzalutamide in any setting will not be eligible.

Exclusion criterion only for patients entering phase Ib expansion cohort:

19. Patients that have received prior taxane-based chemotherapy or abiraterone in any setting will not be eligible for the expansion cohort.

Additional exclusion criterion for patients undergoing tumour biopsy:

Page 42 of 241

Proprietary confidential information. © 2022 Boehringer Ingelheim International GmbH or one or more of its affiliated companies. All rights reserved.

20. For patients that are to undergo the tumour biopsy, a history of a hereditary bleeding disorder, or clinically relevant major bleeding event in the past 6 months, as judged by the investigator.

After approval of protocol version 3 (or subsequent versions) the additional following exclusion criteria apply:

For all patients:

- 21. Previous or concomitant malignancies at any other site with the exception of the following:
 - a.) benign basal cell carcinoma
 - b.) benign low grade transitional cell carcinoma of the bladder
 - c.) other effectively treated malignancy that has been in remission for more than 5 years and is considered to be cured

Only for patients entering phase Ib dose escalation and phase II cohorts:

- 22. Patients who have received more than 2 prior non-docetaxel-containing cytotoxic chemotherapy regimens for Metastatic Castration-Resistant Prostate Cancer (mCRPC).
- 23. Patients who have received a taxane based treatment or abiraterone, within 4 weeks before start of study treatment.

After approval of protocol version 6 (or subsequent versions) the additional following exclusion criteria apply:

Only for patients entering phase Ib dose expansion cohort:

24. Patients that are in immediate need of chemotherapy (e.g. for visceral disease, or intractable pain) should be excluded.

3.3.4 Removal of patients from therapy or assessments

3.3.4.1 Removal of individual patients

A patient must discontinue therapy with the trial drug(s) in case the following apply:

- 1. The patient withdraws consent to further study treatment
- 2. The patient develops unequivocal disease progression, supported by radiological evidence where possible.
- 3. An individual patient violates eligibility criteria which would affect the safety of the patient and/or the patient fails to comply with the protocol (after discussion between the sponsor and the investigator)

Boehringer Ingelheim BI Trial No.: 1280.8

Doc. No.: c02304008-15

Trial Protocol Version 12

06 Jun 2022 Page 43 of 241

Proprietary confidential information. © 2022 Boehringer Ingelheim International GmbH or one or more of its affiliated companies. All rights reserved.

- 4. The patient is receiving forbidden concomitant therapy affecting the safety of the patient according to the judgment of the investigator (refer to section 4.2)
- 5. The patient is no longer able to participate for other medical reasons (e.g. surgery, adverse events, or other diseases)
- 6. The patient meets one of the criteria that require permanent discontinuation of trial drug or dose reductions beyond those specified in section 4.1.4.4
- 7. Investigator and patient (following discussion) consider it in the patient's best interest to remove the patient from BI 836845 following results of the phase II trial.
- 8. The trial is terminated for any of the reasons listed in section 3.3.4.2 "Discontinuation of the trial by the sponsor".

Patients who discontinue or withdraw prior to entering the active treatment phase will be entered in the trial database and will be reported. The data for patients who discontinued or withdrew from the trial after entering the active treatment phase must be documented and the reason for withdrawal must be recorded in the eCRF. These data must be included in the trial database and must be reported.

If an individual patient withdraws consent for further participation in the trial including withdrawal to be followed up, the patient will be asked to have an end of trial investigation and the data collected until the point in time when withdrawal occurred will be included in the final analysis of the trial data. No further follow-up will be done for this patient. However, the investigator will be allowed to report the date and reason of death in case of public registry, or the investigator becomes aware of the date and/or reason for death.

3.3.4.2 Discontinuation of the trial by the sponsor

Boehringer Ingelheim reserves the right to discontinue the trial overall or at a particular trial site at any time for the following reasons:

- 1. Failure to meet expected enrolment goals overall or at a particular trial site,
- 2. Emergence of any efficacy/safety information that could significantly affect continuation of the trial or any other administrative reasons.
- 3. Violation of GCP, the CTP, or the contract by a trial site or investigator, disturbing the appropriate conduct of the trial.
- 4. Discontinuation of the clinical development program with BI 836845 in CRPC.
 - As described in section 2.3 Benefit-risk assessment, topline results of 1280-0022 showed no added benefit of xentuzumab compared to placebo when treating participants with metastatic breast cancer. Consequently, the clinical development of xentuzumab (BI 836845) was discontinued by Boehringer Ingelheim in oncology generally, including in CRPC. Due to the worsening in benefit-risk and the discontinuation of the clinical development program with BI 836845 in CRPC, the trial will proceed towards termination based on the following 3 steps:
 - a. For xentuzumab-treated patients, the xentuzumab treatment will not extend past the drug expiration date (May 2023) of the last planned GMP manufacturing batch of IMP xentuzumab (provided that all patients are on xentuzumab for at least 2 years, and they

Doc. No.: c02304008-15 Page 44 of 241 Proprietary confidential information. © 2022 Boehringer Ingelheim International GmbH or one or more of its affiliated companies. All rights reserved.

are tolerating the drug without tumor progression). Patients that will discontinue xentuzumab can still be eligible for continued treatment with enzalutamide (standard of care in this setting) provided they are tolerating the drug without tumor progression.

- b. When all patients have discontinued xentuzumab treatment, if any patient on enzalutamide is able to continue taking this approved medication off study, then, at the request of the sponsor, the patient may end such treatment as part of the trial and discontinue study participation (if both the Investigator and patient agree).
- c. After all patients end treatment with all study drugs (xentuzumab and enzalutamide), the trial will be terminated.

The investigator / the trial site will be reimbursed for reasonable expenses incurred in case of trial termination (except in case of the third reason).

3.3.5 Replacement of patients

For phase Ib escalation:

Patients will be replaced for determination of the primary endpoint (MTD) in cases of:

- Patient's withdrawal during the first cycle of treatment for reasons other than DLT, e.g. patient no longer wishes to participate, or lost to follow up during first cycle.
- Patients who do not experience DLT, but miss more than one dose of BI 836845 during the first cycle of treatment.
- Patients who do not experience DLT, but miss 3 or more consecutive doses of enzalutamide during the first cycle of treatment.
- Patients who miss one complete cycle at any time beyond the first cycle of treatment may be replaced after discussion between the sponsor and the investigator.
- Patients who are non-evaluable with respect to DLT.
- Patients with CTCAE grade ≥3 allergic reaction/hypersensitivity to the study drug(s) within the first cycle will be replaced.

Patients that have been replaced might continue treatment in the trial should criteria in section 4.1.4.4 apply; however these patients will not be considered for analysis of the primary endpoint of this part.

For phase Ib expansion cohort:

Patients who withdraw after assignment but before start of therapy will be replaced.

BI Trial No.: 1280.8 Doc. No.: c02304008-15

Trial Protocol Version 12 Proprietary confidential information. © 2022 Boehringer Ingelheim International GmbH or one or more of its affiliated companies. All rights reserved.

4. **TREATMENTS**

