5.2.4 Maximum Tolerated Dose (MTD) and Recommended Phase II Dose (RP2D)

The maximum tolerated dose in this study is defined as the highest protocol dose level of BI 836845 in combination with enzalutamide, at which no more than 1 out of 6 patients in a cohort experiences a drug related DLT during the first 28 day treatment cycle – i.e. the incidence of a dose limiting toxicity is no more than 17%. DLT events experienced after the start of the second treatment course will be examined separately.

The MTD or a lower dose level will be chosen as the recommended phase II dose (RP2D) based on the totality of the safety data available at the time that 6 evaluable patients have finished course 1 of treatment at the MTD (or RP2D if MTD not reached); at the earliest. The discussion and agreement on dose selection between the phase Ib escalation investigators and the sponsor will be documented and communicated to all participating sites. The recommended phase II dose (RP2D) will also be used for the phase Ib expansion cohort.

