6.3 PATIENTS SETS ANALYSED

The following analysis sets will be defined for this trial:

• Enrolled set (ENR)

This patient set includes all patients with informed consent given. The enrolled set will be used for patient disposition tables.

• Treated set (TS)

This patient set includes all patients who are documented to have received and taken at least one dose of any study medication during the treatment cycles (from day 1).

In phase Ib escalation and expansion parts, the TS will be used for all planned safety and efficacy analyses, except for CTCs endpoints in phase Ib expansion part, for which the corresponding biomarker set (CTCb) will be used (see below). In phase II part, the TS will be used for all planned safety analyses.

• MTD Set (MS)

The MTD set defines the set of patients in the phase Ib escalation part of the trial that are fully evaluable for determination of the MTD in the first treatment course. The MTD set will be used for some safety analyses in the first part, this is specified in the technical TSAP.

Patients in the TS who were replaced within the MTD evaluation period in the first part of the trial will be excluded from the determination of the MTD. Replacement of patients in the first part of the study is defined in Section 3.3.5 of the CTP. The final list of replaced patients is supplied by the Trial Clinical Monitor (TCM) no later than the last report planning meeting (RPM) before the DBL for the safety analysis.

• Randomised set (RS)

This patient set includes all randomised patients in the phase II of the trial, regardless of whether or not they have received treatment. Patients are assigned to xentuzumab in combination with enzalutamide or enzalutamide alone. The randomised set will be used for the efficacy analyses of patients in the phase II of the study, except for CTCs endpoints, for which the corresponding biomarker set (CTCb) will be used (see below).

^[2] IPV will be identified via individual review at MQRM/RPM/DBL.

^{*} During the amendments of CTP the inclusion and exclusion criteria were adapted. Therefore, the inclusion/exclusion criteria valid at subject's enrolment have to be considered.

• Pharmacokinetic set (PKS)

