7.4 PRIMARY ENDPOINTS

7.4.1 Phase Ib escalation

The primary endpoints are the MTD and the occurrence of DLT. The MTD is determined from the occurrences of DLTs during the MTD evaluation period (this period is defined in Section 5.1.1). An overall summary of the DLTs (see CTP Section 5.2.3 for definitions of DLT) which occurred during the MTD evaluation period and the on-treatment period will be provided for each dose cohort.

Patients that were treated but replaced for the MTD evaluation (see CTP Section 3.3.5) will be excluded from the MTD determination. Replacement of patients will be determined on a case by case basis; exclusion of these patients from the MTD evaluation will be confirmed by the trial team at the RPM prior to DBL.

A listing of patients with DLTs by initial treatment will be performed. A plot with an overview of the phase I escalation part (showing the patients and their assigned doses, replaced patients and patients with DLT) will be displayed.

At the end of the dose escalation phase, a safety analysis will be performed to determine the RP2D. The results will be documented for internal use and communication with the participating investigators (see also Section 9.1).

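### Protocol 3.3.5 lets a patient with a settled cycle-1 DLT outcome be dropped from the MTD analysis for missing a later cycle, while SAP 6.3 and 7.8 keep that patient, so the count against the 1-of-6 limit can change after the MTD window

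*Protocol*

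**What the plan says.** Protocol 5.2.4 takes as the MTD the highest level at which "no more than 1 out of 6 patients in a cohort experiences a drug related DLT during the first 28 day treatment cycle". It puts this limit at an incidence of 17% and has DLTs from the second course onwards examined separately. SAP 5.1.1 ends the MTD evaluation period at the start of cycle 2, or at 28 days if cycle 2 is not started.

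The escalation list in protocol 3.3.5 opens with "Patients will be replaced for determination of the primary endpoint (MTD) in cases of". Most of its bullets concern the first cycle. Three of these exempt patients with a DLT: the withdrawal bullet and the two missed-dose bullets, for example "Patients who do not experience DLT, but miss more than one dose of BI 836845 during the first cycle of treatment". A later bullet reads "Patients who miss one complete cycle at any time beyond the first cycle of treatment may be replaced after discussion" (between sponsor and investigator) and has no such exemption. The section allows replaced patients to continue treatment, "however these patients will not be considered for analysis of the primary endpoint of this part".

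The SAP describes the exclusion three times:

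- 6.3, on exclusion from the MTD set: "Patients in the TS who were replaced within the MTD evaluation period in the first part of the trial will be excluded".
- 7.8: the exclusion covers patients replaced within or before the first treatment cycle.
- 7.4.1: "Patients that were treated but replaced for the MTD evaluation (see CTP Section 3.3.5) will be excluded from the MTD determination". Replacement is settled case by case, and exclusions are confirmed at the report planning meeting before database lock.

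**The concern.** A patient who has completed cycle 1 evaluably, or has had a DLT in it, has a final MTD outcome. Nothing in cycle 2 or later can make that outcome unknown, so a missed later cycle is no reason to discard it. Patients who cannot be evaluated for DLT already have their own bullet in 3.3.5.

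As written, the later-cycle bullet allows a known primary-endpoint result to be removed after the fact, by discretion, in an open-label cohort. It also allows the protocol and the SAP to reach different MTD counts from the same patients. The limit is one DLT in six, so a single patient can decide whether a level passes. The MTD or RP2D in turn sets the dose for the expansion cohort and phase II Arm A (protocol 4.1.4.2 and 5.2.4).

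**Working it through.** **The plan's own figure.** 1/6 = 16.7%, which reproduces the 17% in protocol 5.2.4. One more DLT gives 2/6 = 33%, and the level fails.

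**One patient followed through the texts.** Take a patient who finished cycle 1 and then missed all of cycle 2. Cycle 2 runs from day 29 to day 56, so the ground for replacement is complete only after the MTD evaluation period has closed.

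- Protocol 3.3.5: may be replaced; if replaced, out of the MTD analysis.
- SAP 6.3: not replaced within the evaluation period, so in.
- SAP 7.8: not replaced within or before cycle 1, so in.
- SAP 7.4.1: out if the reference to 3.3.5 covers every bullet; in if replacement for the MTD evaluation means replacement during that period.

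**Effect on the count.** Assumptions: true cycle-1 DLT probability p, not given in the documents and taken as 0.2 to 0.4; the replacement patient has the same p; one replacement per level, after six patients. At the highest dose, protocol 4.1.3.3 adds three patients only if at most one of the first three has a DLT. Two DLTs in six therefore arise as 0 then 2, or 1 then 1.

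- A = P(at most 1 of 6) = (1−p)^6 + 6p(1−p)^5
- B = P(2 of 6 by those paths) = (1−p)^3 · 3p²(1−p) + [3p(1−p)²]²
- C = P(1 of 6) = 6p(1−p)^5

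If every level in B has one DLT patient replaced, the new count is 1 of 6 with probability 1−p, and the pass probability becomes A + B(1−p). If every level in C has one non-DLT patient replaced, the new count is 2 of 6 with probability p, and the pass probability becomes A − Cp.

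At p = 0.3:

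- A = 0.118 + 0.303 = 0.420
- B = 0.343 × 0.189 + 0.441² = 0.065 + 0.194 = 0.259
- Upward: 0.420 + 0.259 × 0.7 = 0.602
- Downward: 0.420 − 0.303 × 0.3 = 0.329

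| p | A | B | A + B(1−p) | C | A − Cp |
|---|---|---|---|---|---|
| 0.2 | 0.655 | 0.197 | 0.813 | 0.393 | 0.577 |
| 0.3 | 0.420 | 0.259 | 0.602 | 0.303 | 0.329 |
| 0.4 | 0.233 | 0.249 | 0.383 | 0.187 | 0.159 |

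(Results computed before rounding.) If only cycle-1 evaluability decides membership, column A applies and later events cannot move it.

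**Can a cycle-1 DLT lead to a missed cycle 2?** In escalation both drugs are paused for a drug-related DLT (protocol 4.1.4.4), and Table 4.1.4.4:1 allows 28 days for recovery before permanent discontinuation. Cycle 2 infusions fall on days 29, 36, 43 and 50. A pause from day 22 reaches 22 + 28 = day 50, so the last infusion could still be given. A pause from day 23 reaches day 51 and covers all four. The route is open, but only for a DLT in about the last week of cycle 1 with close to the maximum recovery time. The table's footnote on continued treatment for clinical benefit could widen it.

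**The case against.** The strongest reply is that the bullet would rarely have an effect. Replacement is permissive and needs discussion. Escalation decisions follow completed first cycles (protocol 4.1.4.1 and 5.2.3), usually before a later cycle could be missed. The RP2D rests on the totality of the safety data (5.2.4), and SAP 5.1.1 includes later DLTs in that basis. DLTs are tabulated both for the first course and overall (protocol 7.3.3), and SAP 7.4.1 plans a plot of replaced patients and patients with DLT. A dropped DLT would thus stay visible. All of this stands and limits the practical harm.

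It is also fair that the SAP can be read as consistent. Section 6.3 itself points to protocol 3.3.5 for what replacement means, so the same pointer in 7.4.1 need not widen the exclusion. A reader might infer that the SAP flatly contradicts itself; the text supports only an ambiguity in 7.4.1.

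A reader might also infer a bias towards declaring the highest dose tolerable. The documents do not show this. Replacing a non-DLT patient moves the count the other way, and the link from a cycle-1 DLT to a missed cycle is narrow.

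The reply does not remove the mismatch between protocol 3.3.5 and SAP 6.3 and 7.8. Nor does it supply the DLT exemption that the later-cycle bullet lacks.

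**Conclusion.** The point holds as a defect in the rule. Protocol 3.3.5 permits a known cycle-1 result, including a DLT, to be removed from the MTD analysis for an event after the MTD window. SAP 6.3 and 7.8 would keep that patient, and SAP 7.4.1 is unclear. The count can then cross the limit in either direction.

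The rise from 0.42 to 0.60 at p = 0.3 (0.66 to 0.81 at 0.2; 0.23 to 0.38 at 0.4) is a ceiling for one scenario: every highest-dose level with 2 DLTs in six has one DLT patient replaced. The matching fall at p = 0.3, if every level with 1 of 6 has a non-DLT patient replaced, is from 0.42 to 0.33. Neither is an estimate, because the DLT rate and the frequency of later missed cycles are not given. A reader might also infer that the dose taken forward was affected; the documents do not say that any patient was replaced on this ground.

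The change is worth making because the MTD is the primary endpoint of this part and the repair is small.

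**What to change.** Reconcile protocol 3.3.5 with SAP 6.3, 7.4.1 and 7.8 so that one rule defines the MTD set: a patient who completed cycle 1 evaluably, or had a DLT in it, stays in whatever happens later. Delete the later-cycle bullet from 3.3.5 or limit it to purposes other than the MTD. Put the time limit of SAP 6.3 into 7.4.1.

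Escalation is complete and its safety analyses are already documented (SAP section 3), so new wording cannot alter the dose decision. The useful step now is disclosure: state whether any escalation patient was replaced under this bullet and, if so, report the MTD count with that patient retained. The report revision foreseen in protocol 2.2 can carry this.

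The cost is one protocol bullet, one SAP sentence and one statement in the report, with no additional patients. If nobody was replaced on this ground, that statement closes the matter.
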